Of primary exploratory interest is the overall incidence of ALL CIN 2/3 and invasive cervical cancer (caused by any vaccine or non-vaccine HPV type). Several other exploratory endpoints will be evaluated including: (1) CIN 2/3 or worse related to HPV 16 and 18 separately; (2) vaccine-type-HPV-related CIN 1 or worse; (3) CIN 1 or worse due to any cause; (4) HPV 6/11-related genital warts; (5) any HPV 6/11/16/18-related lesion; (6) any HPV-related lesion; (7) colposcopy; (8) colposcopic biopsy due to any CIN; (9) definitive therapy due to any CIN; and (10) Pap abnormalities. In addition, the antibody responses in vaccine recipients who have breakthrough cases of HPV 16/18-related CIN 2/3 or worse will be evaluated. The potential therapeutic effects of administering the quadrivalent HPV (Types 6, 11, 16, 18) L1 VLP vaccine to subjects who are already infected at baseline with a vaccine HPV type, but who have not yet mounted an immune response to the HPV infection, will be assessed. The time-to-event (or disease-free time) distributions in the vaccine and placebo groups will be compared. Finally, an observational assessment of a potential waning in vaccine efficacy will be performed.

B. Study Participant Populations for Efficacy Analyses

Four patient populations will be considered for the efficacy analyses: 1 per-protocol population and 3 modified intention-to-treat (MITT) populations.

B. Study Participant Populations for Efficacy Analyses (Cont.)

The efficacy analysis using the per-protocol population will be the primary analysis. Supplemental analyses of the primary and secondary efficacy endpoints will be provided using the 3 MITT populations. The populations that will be considered for the exploratory efficacy endpoints are described in their respective sections.

The per-protocol and MITT populations differ with regard to the inclusion/exclusion of protocol violators who are described below.

Per-Protocol Population

To be included in the per-protocol analyses, subjects must:

1. receive all 3 injections with the correct dose of the correct clinical material;
2. be seronegative by RIA to the appropriate HPV types before the first injection and PCR-negative to the appropriate HPV types through Month 7;
3. not receive any nonstudy inactivated vaccine within 14 days of a study vaccine or any nonstudy live virus vaccine within 21 days before or 14 days after a study vaccine;

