to all CIN (any grade due to any cause) will be estimated. Point estimates and confidence intervals for the vaccine efficacy will be provided using the methodology described above for the primary analyses. The HPV 16- or 18-related CIN 1 or worse endpoint and the HPV 6/11/16/18-related CIN 1 or worse endpoint will be summarized in the per-protocol and the first MITT population. To be included in the analysis of CIN due to any cause, subjects will be required to be seronegative and PCR negative from Day 1 through Month 7 for relevant HPV types or have normal Pap test results from Day 1 through Month 7 and a history of normal Pap test results (see Section III.B.). Only point estimates of the vaccine efficacy and 95% confidence intervals for the efficacy with respect to these endpoints will be provided. No statistical testing will be conducted.

f. Other HPV-Related Lesions

The impact of the vaccine on other HPV-related lesions and other combinations of HPV-related lesions will also be evaluated. The person-time based incidences of: (1) HPV 6- or 11-related external genital warts; (2) any HPV 6, 11, 16, or 18-related lesion; and (3) any HPV-related lesion will be estimated by treatment group. Corresponding 95% confidence intervals for the incidence rates will be provided. To be eligible to be counted as an HPV 6/11-related endpoint, subjects will be required to be seronegative at Day 1 and PCR negative from Day 1 through Month 7 for HPV 6 and HPV 11. To be eligible to be counted as an HPV 16- or 18-related endpoint, subjects will be required to be seronegative at Day 1 and PCR negative from Day 1 through Month 7 for the relevant type. To be eligible to be counted as an endpoint related to other HPV types, subjects will be required to be PCR negative from Day 1 through Month 7 for the relevant HPV types or have normal Pap test results from Day 1 through Month 7 and have a history of normal Pap test results (see Section III.B.). Only point estimates of the incidence rates and 95% confidence intervals for the rates with respect to these endpoints will be provided. No statistical testing will be conducted.

g. Gynecologic Procedures

The efficacy of the quadrivalent HPV (Types 6, 11, 16, 18) L1 VLP vaccine in reducing the incidence of: (1) colposcopy, (2) colposcopic biopsy due to any CIN, and (3) definitive therapy due to any CIN will be estimated using the same methodology that will be used for the

C. Approaches to Efficacy Analysis (Cont.)

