primary analysis. Only point estimates of the vaccine efficacy and 95% confidence intervals for the efficacy with respect to this endpoint will be provided. Estimates will be provided using the per-protocol and all of the MITT populations. No statistical testing will be conducted.

h. Pap Abnormalities

Person-time based incidences of the following Pap abnormalities will be summarized by treatment group: (1) high-grade squamous intraepithelial lesion (HSIL) or worse, (2) low-grade squamous intraepithelial lesion (LSIL) or worse, (3) atypical squamous cells of undetermined significance (ASC-US) with positive HPV probe or worse (atypical squamous cells suggestive of a high-grade intraepithelial lesion [ASC-H], HSIL, LSIL, Atypical Glandular Cells), and (4) ASC-US or worse. To be included in these summaries, subjects will be required to be seronegative and PCR negative from Day 1 through Month 7 to all HPV types for which subjects are tested, have normal Pap test results from Day 1 through Month 7, and have a history of normal Pap test results. The incidences of the above Pap abnormalities will also be summarized in subjects who are seronegative and PCR negative at Day 1 to all HPV types for which subjects are tested, have normal Pap test results at Day 1, and have a history of normal Pap test results. Only point estimates of the incidence rates and 95% confidence intervals for the rates with respect to these endpoints will be provided. These evaluations will be conducted on the subsets of subjects above both including and excluding general protocol violators. No statistical testing will be conducted.

i. Potential Therapeutic Effect of the Vaccine

Data permitting, an exploratory analysis to assess the potential therapeutic effects of administering the quadrivalent vaccine to subjects who are already infected with a vaccine HPV type, but who have not yet mounted an immune response to the HPV infection at baseline, will be performed. Specifically, the vaccine's impact in reducing the incidence of (1) HPV 16- and 18-related CIN 2/3 or worse and (2) HPV 6-, 11-, 16- and 18-related CIN 1 or worse will be evaluated in these subjects.

C. Approaches to Efficacy Analysis (Cont.)

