For example, among subjects HPV 16 seronegative and PCR positive at Day 1 or HPV 18 seronegative and PCR positive at Day 1, the incidence of CIN 2/3 related to the relevant HPV type will be estimated in each treatment group and the 95% confidence intervals for these rates will be provided. Only cases of CIN that are detected following the Month 7 visit will be included in this analysis.

j. Assessment of Potential Waning of Vaccine Efficacy

Due to the timing between the development of HPV infection and the development of clinical sequelae, it is expected that the target number of cases required to estimate the vaccine efficacy with respect to the primary endpoint of the study at the interim analysis (19 cases) will be observed ~2.5 years into the study. By Year 4, it is anticipated that ~10 to 12 additional cases will be observed. Thus, there is limited power in this study to draw any definitive conclusions regarding changes in vaccine efficacy over time. Nevertheless, an exploratory analysis will be conducted to assess a possible waning of the vaccine efficacy. Specifically, at the conclusion of the study, the vaccine efficacy by year will be estimated, and any observed trends in the efficacy over time will be reported. The first year estimate will include all follow-up through Month 12 for each subject; the second year estimate will include all follow-up through Month 24 for each subject; the third year estimate will include all follow-up through Month 36 for each subject; and the final estimate will include all follow-up through Month 48 for each subject. A potential waning of vaccine efficacy will be explored using the per-protocol and first MITT populations.

D. Definition of Compliance Measure

Treatment compliance is defined in this study as receipt of all scheduled study vaccinations. To summarize treatment compliance, the numbers of subjects who receive each vaccination will be tabulated by treatment group. As stated in Section III.B., subjects who do not complete the full vaccination regimen will be excluded from the per-protocol primary analyses of efficacy but will be included in 2 MITT analyses.

Another important compliance measure in this study is the degree of subject compliance with follow-up visits following the completion of the vaccination series. Since colposcopy is a required procedure for the identification of potential study endpoints, subjects who miss study follow-up visits or who

D. Definition of Compliance Measure (Cont.)

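### Section III.C.3.f evaluates the vaccine's impact on genital warts and other lesions without an interval for the vaccine-placebo contrast; sections h and i have a related, weaker gap

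*SAP*

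**What the plan says.** The three sections sit under Exploratory Efficacy Analyses and differ in aim and in how firmly they limit the output.

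- **III.C.3.f, Other HPV-Related Lesions.** The aim is comparative: "The impact of the vaccine on other HPV-related lesions and other combinations of HPV-related lesions will also be evaluated". The output is person-time incidence by treatment group, and the section closes the list: "Only point estimates of the incidence rates and 95% confidence intervals for the rates with respect to these endpoints will be provided".
- **III.C.3.h, Pap Abnormalities.** The aim is descriptive: "Person-time based incidences of the following Pap abnormalities will be summarized by treatment group". The same limiting sentence follows.
- **III.C.3.i, Potential Therapeutic Effect of the Vaccine.** The aim is comparative: "Specifically, the vaccine's impact in reducing the incidence of (1) HPV 16- and 18-related CIN 2/3 or worse", and likewise for vaccine-type CIN 1 or worse, in women infected but seronegative at baseline. The analysis depends on the data permitting it. The only output described is an example, in which incidence "will be estimated in each treatment group and the 95% confidence intervals for these rates will be provided".

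Section III.A (Efficacy Endpoints) lists warts, the lesion composites and Pap abnormalities among the exploratory efficacy endpoints ("Several other exploratory endpoints will be evaluated including: (1) CIN 2/3 or worse related to HPV 16 and 18 separately"). It says of the therapeutic effect in infected women "but who have not yet mounted an immune response to the HPV infection, will be assessed".

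**The concern.** Subjects are randomised 1:1 to vaccine or placebo, and the vaccine's impact on an endpoint is a comparison of the arms. An incidence rate with its own interval in each arm is not an interval for that comparison. A reader left with two such intervals may judge the effect by whether they overlap, which is a less sensitive guide than the interval for the contrast. A real effect could then look inconclusive. Where little or no effect is seen, as may happen in already-infected women, the per-arm output does not properly bound how large a benefit or harm remains possible.

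The wart result also bears on the SAP's own reasoning. Section VII.D.1.e (Ascertainment Bias) excludes cases found at colposcopies done solely for warts, because bias would arise if the vaccine works against warts. VE against warts with an interval would show readers how far that condition holds.

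**Working it through.** **1. What each exploratory section plans**

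| Section III.C.3 | Endpoint | Planned output | Testing |
|---|---|---|---|
| a | All CIN 2/3 or cancer | VE, 95% CI | none |
| b | Primary endpoint by HPV type | VE, 95% CI | none |
| e | CIN 1 or worse; all CIN | VE, 95% CI | none |
| f | Warts; vaccine-type lesions; any HPV lesion | per-arm rates, 95% CIs, nothing else | none |
| g | Colposcopy, biopsy, definitive therapy | VE, 95% CI | none |
| h | Pap abnormalities | per-arm rates, 95% CIs, nothing else | none |
| i | CIN in women infected at baseline | per-arm rates, 95% CIs, as an example | not mentioned |

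Neither exploratory status nor the absence of testing explains the split. Sections a, b, e and g share both features and still give VE with an interval.

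**2. The SAP's method, checked against its own figures**

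Section VII.D.1.a conditions on the total number of cases T. With equal follow-up, the vaccine count is Binomial(T, p) with p = (1 − VE)/(2 − VE), and VE limits are (1 − 2p)/(1 − p) at the exact limits of p. Using the alphas of section VII.E, the largest vaccine count that succeeds is 4 of 19 (interim) and 8 of 29 (final).

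| True VE | Interim: Table 7 | Recomputed | Final: Table 7 | Recomputed |
|---|---|---|---|---|
| 80% | 80% | 80.1% | 95% | 95.9% |
| 85% | 90% | 90.9% | 99% | 99.1% |
| 90% | 97% | 97.6% | >99% | 99.9% |

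Each figure agrees within one percentage point, so the method is read correctly.

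**3. Per-arm intervals against the VE interval**

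The counts are assumed, because the SAP gives no expected counts for these endpoints. Follow-up is taken as equal. Arm intervals are exact Poisson 95% limits on the case count.

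For 8 vaccine and 20 placebo cases:
- Arm intervals are 3.5 to 15.8 and 12.2 to 30.9 cases. They overlap.
- VE = 1 − 8/20 = 60%.
- The exact limits of p are 0.132 and 0.487. The VE limits are (1 − 2 × 0.487)/(1 − 0.487) ≈ 5% and (1 − 2 × 0.132)/(1 − 0.132) ≈ 85%.

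Combining opposite ends of the arm intervals does not recover the VE interval:

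| Cases, vaccine vs placebo | VE | Exact 95% CI | From combined interval ends |
|---|---|---|---|
| 5 vs 15 | 66.7% | 3.5% to 90.5% | −39.0% to 93.4% |
| 10 vs 24 | 58.3% | 9.6% to 82.2% | −19.6% to 86.6% |
| 30 vs 52 | 42.3% | 7.9% to 64.5% | −10.3% to 70.3% |
| 20 vs 20 | 0% | −96% to 49% | −153% to 60% |

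**4. How the gap depends on case count and effect**

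These are binomial probabilities that the VE interval excludes 0, and that the two arm intervals separate.

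| Total cases | True VE | VE interval excludes 0 | Arm intervals separate |
|---|---|---|---|
| 15 | 80% | 77% | 26% |
| 29 | 60% | 55% | 24% |
| 29 | 70% | 79% | 48% |
| 29 | 80% | 96% | 80% |
| 60 | 70% | 99% | 92% |
| 100 | 70% | 100% | 99.8% |
| 100 | 60% | 99% | 94% |
| 100 | 40% | 66% | 34% |

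The gap is wide with few cases or a weak effect and nearly closes with many cases and a strong one.

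**The case against.** A reader might infer that all three sections forbid a comparison and that the vaccine effect is never estimated. The SAP does not support that reading.

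- Section h delivers the summary it promises. Its efficacy purpose comes from the endpoint list in III.A and from its place among the efficacy analyses.
- Section i contains no limiting word, and its per-arm rates are an illustration. It is underspecified, not restricted.
- The two rates give the VE point estimate directly, by the formula in VII.D.1.a. The missing item is the interval. Even that could be computed if case counts and person-years are tabulated.

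The stated primary, secondary and exploratory efficacy objectives (sections I.B.3 to I.B.5) do not mention warts, Pap results or a therapeutic effect. Neighbouring ground is partly covered: section e gives VE for the cervical components of the lesion composites, and section g gives VE for the procedures that follow abnormal Pap tests.

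The figures in step 4 also rest on a reading by overlap that the SAP nowhere adopts, and on assumed counts. Of these, 29 is the trigger for the rarer primary endpoint.

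All of this stands, and it narrows the point. It does not explain why section f announces an evaluation of impact and then excludes the interval that its neighbours report.

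**Conclusion.** The point holds as a minor inconsistency. It is firm for section f, where a comparative aim meets an output limited to per-arm rates. For section h the same limit applies to an endpoint that III.A lists under efficacy, but there is no mismatch inside the section. For section i the contrast is left unspecified. What is missing is the interval for VE, because the point estimate can be derived.

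The size of the loss cannot be fixed from the SAP. It rests on assumed case counts, equal follow-up and a reader who judges by overlap. Under those assumptions it ranges from large (15 cases, VE 80%: 77% versus 26%) to negligible (100 cases, VE 70%: 100% versus 99.8%). The primary and secondary efficacy analyses estimate VE between the randomised arms and are untouched.

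**What to change.** In sections III.C.3.f, h and i, state that VE and its exact 95% confidence interval, by the method of section VII.D.1.a, will be reported alongside the per-arm incidence rates, descriptively and without testing, as in sections e and g. In f and h this replaces the limiting sentence; in i it supplies the contrast that the text leaves open.

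The cost is one sentence in each of three subsections. The method is already specified for the primary analysis and no further data are needed. The downside is a few more descriptive intervals without multiplicity control, which sections a, b, e and g already accept.

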Protocol 015 is a prospective randomized, double-blind, placebo-controlled, parallel, multicenter study operating under in-house blinding procedures. Embedded within Protocol 015 is a consistency lot substudy. Approximately 11,500 subjects will be randomized in a 1:1 ratio to receive either 3 injections of quadrivalent HPV (Type 6, 11, 16, 18) L1 VLP vaccine or 3 injections of placebo. Within the quadrivalent HPV vaccine group, subjects will be further randomized to receive 3 different lots of the vaccine in a 1:1:1 ratio. The actual lots received will differ between subjects enrolled in the consistency lot substudy and the remaining subjects in Protocol 015. Each dose of quadrivalent vaccine will contain 20 µg HPV 6 L1 VLP, 40 µg HPV 11 L1 VLP, 40 µg HPV 16 L1 VLP, and 20 µg HPV 18 L1 VLP. Vaccine or placebo is administered at 0, 2, and 6 months. Approximately 1 month following the third vaccination visit (Month 7), 6 months following the third vaccination visit (Month 12) and every year thereafter until Month 48, subjects will return to the study center for collection of specimens, gynecologic examinations and Pap tests. Subjects with Pap test abnormalities at scheduled visits will be referred for colposcopy based on a mandatory triage strategy. Lesions observed during the colposcopy will be biopsied. Sections of each biopsy will be sent to members of the Pathology Panel for pathological diagnosis. Additional sections will be sent to Merck Research Laboratories (MRL) for PCR analysis. Should a subject be referred for definitive therapy based on a diagnosis of CIN 2/3 or worse, sections of the tissue excised during the definitive therapy procedure will be sent to the Pathology Panel for diagnosis. Additional sections will be sent to MRL for PCR analysis.

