the vaccine and placebo groups. Kaplan-Meier (product limit) estimates of the time-to-event curves and the corresponding 95% confidence intervals will be displayed by treatment group, and the estimated time-to-event curves will be plotted. The time-to-event distributions between the 2 treatment groups will be compared using the log-rank test. The log-rank statistic and the corresponding p-value will be noted on the plot of the curves. For each subject who meets the endpoint definition, the time-to-event will be the time between the subject's Month 7 visit date and the earliest date a tissue sample is collected from the subject which meets the endpoint criterion. For all other subjects, the time between the subject's Month 7 visit date and the date the subject (1) drops out of the study, (2) has definitive therapy, or (3) completes the study will be used in the analysis. The time-to-event analysis will be conducted for the per-protocol and the 3 MITT populations.

d. Correlates of Protection

An exploratory analysis of any breakthrough HPV 16/18-related CIN 2/3 or worse cases (cases of HPV 16/18-related CIN 2/3 or worse in vaccine recipients) will be performed to try to establish the relationship between immune markers and protection from disease endpoints. Specifically, the immune responses in the non-breakthrough vaccinees will be compared with the immune responses in the breakthrough cases at all available time points (i.e., at Months 7, 24, and 48). However, if there are few cases among the vaccine recipients, there may be insufficient information to establish an immune correlate of protection in this study.

Immune markers will be explored using the per-protocol population. However, if the vaccine is highly efficacious, very few primary endpoints will be observed in the vaccine group in the per-protocol analysis. If this is the case, it may be more informative to explore correlates of protection in the second MITT population. This population still includes only initially HPV naïve subjects but is likely to yield the most endpoints in the vaccine group.

e. CIN 1 or Worse

The vaccine efficacy with respect to the incidence of HPV 16- or 18-related CIN 1 or worse and HPV 6-, 11-, 16- or 18-related CIN 1 or worse will be estimated. In addition, the vaccine efficacy with respect

C. Approaches to Efficacy Analysis (Cont.)

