In the primary per-protocol analysis, follow-up for CIN 2/3 and cervical cancer begins following the Month 7 visit. Therefore, each subject's follow-up time will be computed by calculating the number of days between her Month 7 visit date and her final visit date. For cases, the "final visit" will be the first visit at which CIN 2/3 or cervical cancer was detected for the purpose of person-time computation. This value will be converted to person-years by dividing by 365.25. To obtain the total follow-up time in each treatment group, k_v and k_p , the person-years will be summed over all subjects in the given treatment group.

Although the primary analysis is per-protocol and HPV type-specific, all subjects who are eligible for the per-protocol analysis based on at least 1 of the 2 HPV types being analyzed (HPV 16 or 18) will contribute follow-up time to the totals. For the exploratory analysis of all CIN 2/3, all subjects who are eligible for the per-protocol analysis based on at least 1 high-risk HPV type will contribute follow-up time to the totals.

d. Correlates of Protection

In addition to the methods described in Section III.C.3.c. for assessing the anti-HPV serum RIA responses as potential correlates of protection, the odds of developing breakthrough HPV 16/18-related CIN 2/3 or worse may be modeled as a function of the corresponding Postdose 3 RIA titers using a logistic regression model. Length of postvaccination follow-up and study site will be included as additional model terms. Statistical significance of the coefficient for the RIA titer will be an indication that RIA titer is a predictor of breakthrough

D. Statistical Methods (Cont.)

infection. The estimate of the coefficient will indicate the nature of the relationship. If there are few cases among the vaccine recipients, there may be insufficient information to establish an immune correlate of protection in this study.

e. Potential Bias**1) Ascertainment Bias**

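### Efficacy against any-cause colposcopy is estimated only in populations with no Pap condition, so in the per-protocol analysis colposcopy for disease already present at Month 7 counts as new

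*SAP*

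**What the plan says.** Section III.C.3.g names three exploratory endpoints, "1) colposcopy, (2) colposcopic biopsy due to any CIN, and (3) definitive therapy due to any CIN will be estimated using the same methodology" as the primary analysis. On populations it says only "Estimates will be provided using the per-protocol and all of the MITT populations". It gives point estimates and 95% confidence intervals, without testing.

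Section III.B defines those populations. The only per-protocol criterion on HPV or disease status is to "be seronegative by RIA to the appropriate HPV types before the first injection and PCR-negative to the appropriate HPV types through Month 7". The first and second MITT populations also rest on serology and PCR, and the third takes women regardless of both.

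On the start of follow-up, VII.D.1.c states: "In the primary per-protocol analysis, follow-up for CIN 2/3 and cervical cancer begins following the Month 7 visit". On how women reach colposcopy, the Executive Summary (Study Design) states: "Subjects with Pap test abnormalities at scheduled visits will be referred for colposcopy based on a mandatory triage strategy". Pap tests are taken at Month 7 and at later visits (I.B.1).

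The next section, III.C.3.h, covers Pap abnormalities. It requires women to be negative to all tested HPV types and to "have normal Pap test results from Day 1 through Month 7, and have a history of normal Pap test results". It also defines a second population with the same conditions applied at Day 1 only, again with a normal Pap history.

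**The concern.** For the primary endpoint the type-specific rule does its job: a lesion counts only if the woman was negative for the type found in it. Colposcopy cannot be attributed to a type, so the same filter does not separate procedures for new disease from procedures for disease present when follow-up starts. An abnormal Pap at the Month 7 visit marks time zero and also triggers a colposcopy that then counts as an incident event.

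The neighbouring any-cause analyses guard against this. Sections III.C.3.e and f require women to be naive to the relevant types or to have normal Paps through Month 7 with a normal history. Section III.C.3.h requires both. Section III.C.3.g states no such condition and plans no supporting estimate in Pap-normal women. What is at stake is the reading of an exploratory estimate: a low figure for colposcopy could reflect weak protection or a large share of procedures that no prophylactic effect could have prevented.

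**Working it through.** **1. Where a Pap condition appears**

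- III.C.3.e and f, endpoints not tied to a vaccine type: naive to relevant types, or normal Paps Day 1 to Month 7 plus normal history.
- III.C.3.h, Pap abnormalities: naive to all tested types, and normal Paps (Day 1 to Month 7, or Day 1 only), and normal history.
- III.C.3.g, colposcopy and procedures due to any CIN: none stated.
- VIII.E.2.f, under per-protocol exclusions: concerns prior abnormal Pap or biopsy history, and only analyses of types without an assay. It does not address the Day 1 or Month 7 Pap.

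**2. What the HPV 16/18 filter leaves in**

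Inputs from VII.A.1: 11,500 enrolled; 15% attrition to Month 7; 18% positive for HPV 16; 18% positive for HPV 18; 8% positive for both.

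- Plan's figure reproduced: 11,500 × 0.85 × (1 − 0.08) = 8,993, against about 9,000 stated.
- Positive to exactly one type: 0.18 + 0.18 − 2 × 0.08 = 0.20 of women. They remain in the population at risk and form 0.20 / 0.92 = 21.7% of it.

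III.B assigns this population to the primary endpoint and to procedures due to HPV 16/18 disease. It does not say that III.C.3.g uses it, so the 21.7% applies only if it does. Even then it measures retained HPV-positive women, not abnormal Paps.

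**3. Direction and size of the dilution**

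Let f be the share of placebo-arm procedures that are for existing disease, VE_new the efficacy against procedures for new disease and VE_ex the efficacy against procedures for existing disease. With the same proportion of existing disease in both arms:

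observed VE = (1 − f) × VE_new + f × VE_ex

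If VE_ex = 0, this is VE_new × (1 − f). For an assumed VE_new of 30%, it gives 28.5% (f = 5%), 27% (10%), 24% (20%), 21% (30%) and 15% (50%).

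To express f through rates, let b be the share of women with an abnormal Pap at Day 1 or Month 7, q the share of those who have a colposcopy after Month 7, and r the incidence in other placebo women:

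1 − f = (1 − b)r / [(1 − b)r + bq]

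The SAP gives none of b, q, r or VE_new. Assume VE_new = 25% and r = 10%.

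With q = 50%:
- b = 5%: 25% × 0.095 / 0.120 = 19.8%
- b = 10%: 25% × 0.090 / 0.140 = 16.1%
- b = 15%: 25% × 0.085 / 0.160 = 13.3%

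With q = 20%:
- b = 5%: 25% × 0.095 / 0.105 = 22.6%
- b = 15%: 25% × 0.085 / 0.115 = 18.5%

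The relative loss is about 21 to 47% in the first set and about 10 to 26% in the second. The choice of q alone roughly halves it, so the direction is informative and the size is not.

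**The case against.** The strongest reply is that III.B already has an any-cause rule. For CIN and cancer due to any cause, eligibility requires PCR negativity through Month 7 for the relevant type among 13 tested types; for other high-risk types it requires normal Paps through Month 7 and a normal history. Biopsy and definitive therapy due to any CIN can plausibly be read as falling under it. This stands in part. A reader might infer that all three endpoints are unprotected, but the SAP does not settle that for these two; III.C.3.g simply gives no cross-reference. The reply does not reach colposcopy, because the rule works through the type found in a lesion.

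Second, a reader might infer that all four populations start at Month 7 and are all wrongly chosen. The Month 7 start is explicit for the per-protocol method and for the Kaplan-Meier analysis of the primary endpoint, where "The time-to-event analysis will be conducted for the per-protocol and the 3 MITT populations". The person-time start of the second and third MITT populations for procedures is not stated. The third includes existing disease by design, and any-cause procedure burden is a legitimate question.

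Third, it is tempting to say that a prophylactic vaccine cannot affect existing abnormalities and that they fall equally on both arms. III.C.3.i treats a therapeutic effect as open. An abnormal Month 7 Pap may also reflect infection acquired after dose 1, so randomisation does not guarantee balance. For the same reason, a population selected on Month 7 cytology conditions on a post-randomisation result. These points stand and shape the fix.

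**Conclusion.** The point holds for colposcopy in the per-protocol analysis: no Pap condition, no type to filter on, follow-up from Month 7, and mandatory referral after an abnormal scheduled Pap. The estimate is pulled toward zero to the extent that the vaccine leaves existing disease unaffected and that such disease is similar in both arms. For biopsy and definitive therapy due to any CIN, the finding is an ambiguity about whether III.B applies.

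The size cannot be derived from the SAP, and a reader should not take any of the assumed losses as an estimate. Nor should a reader infer a threat to the trial's conclusions: these endpoints are exploratory and untested, so no error rate or success criterion is affected. This is a worthwhile minor improvement.

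**What to change.** In III.C.3.g:

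1. Add estimates for the three procedure endpoints in both populations of III.C.3.h: (a) negative to all tested types with normal Paps from Day 1 through Month 7 and a history of normal Paps; (b) the Day 1-only version, also with a normal history, which avoids selecting on Month 7 cytology. Report these as the prophylactic estimates beside the planned ones.
2. Keep the third MITT analysis and label it as overall impact.
3. State whether the III.B any-cause rule governs biopsy and definitive therapy due to any CIN.
4. State when person-time starts in each population used for these endpoints.

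Day 1 and Month 7 Paps are collected and both subsets are already needed for III.C.3.h, so the cost is SAP wording and further runs of an existing analysis. The downside is fewer women and events, and so wider intervals, in the added estimates.
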